6.4.6 Deaths

For this study, mortality is an efficacy endpoint. Deaths that occur during the protocol-specified AE reporting period (see Section 6.3.1) that are attributed by the investigator solely to progression of hematological malignancy under current investigation should be recorded only on the Study Completion/Early Discontinuation CRF. All other on-study deaths, regardless of their relationship to the study drug, must be recorded on the AE CRF and immediately reported to the sponsor (see Section 6.5.1).

Death should be considered an outcome and not a distinct event. The event or condition that caused or contributed to the fatal outcome should be recorded as the single medical concept on the AE CRF. Generally, only 1 such event should be reported. The term “sudden death” should only be used for the occurrence of an abrupt and unexpected death due to presumed cardiac causes in a patient with or without pre-existing heart disease, within 1 hour of the onset of acute symptoms or, in the case of an unwitnessed death, within 24 hours after the patient was last seen alive and stable. If the cause of death is unknown and cannot be ascertained at the time of reporting, “unexplained death” should be recorded on the AE CRF. If the cause of death later becomes available (eg, after autopsy), “unexplained death” should be replaced by the established cause of death.

6.4.7 Preexisting Medical Conditions

A preexisting medical condition is present at the start of the study. Such conditions should be recorded on the CRF.

A preexisting medical condition should be recorded as an AE or SAE only if the frequency, severity, or character of the condition worsens during the study. When recording such events on an AE/SAE CRF, it is important to convey the concept that the pre-existing condition has changed by including applicable descriptors (eg, “more frequent headaches”).

6.4.8 Worsening of Hematologic Malignancy

Worsening and/or progression of the hematologic malignancy (eg, leukemia or lymphoma) should not be recorded as an AE or SAE, unless the progression directly leads to the patient’s death, in which case the disease progression should be reported as a CTCAE Grade 5 SAE. All worsening and/or progression of the hematologic malignancy data will be captured as efficacy assessment data.

Hospitalization due solely to the progression of underlying lymphoma should not be reported as an SAE. Clinical symptoms of progression may be reported as AEs if the symptom cannot be determined as exclusively due to the progression of the underlying malignancy or does not fit the expected pattern of progression for the disease under study.

Symptomatic deterioration may occur in some patients. In this situation, progression is evident in the patient’s clinical symptoms but is not supported by the tumor measurements, or the disease progression is so evident that the investigator may elect not to perform additional disease assessments. In such cases, the determination of clinical progression is based on symptomatic deterioration. These determinations should be a rare exception, as every effort should be made to document the objective progression of underlying malignancy.

If there is any uncertainty about an AE being related only to the disease under study, it should be reported as an AE or SAE.

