4.5 Dose Expansion Stage (Stage 2)

The safety, tolerability, PK, and preliminary efficacy of HMPL-523 at the MTD/RP2D, which has been determined to be 700 mg once daily, will be further evaluated in patients with relapsed or refractory non-Hodgkin’s and Hodgkin’s lymphomas.

Amendment 4:

As described in Amendment 4, based on strategic evaluation of the development of HMPL-523, the selected lymphoma cohorts were closed as of 30 November 2022: MCL, FL, MZL, WM/LPL, PTCL, and CBCL. Enrollment was continued in the CLL and HL cohorts.

The number of patients enrolled in each cohort as of Amendment 5 is shown in [Table 2](#).

Amendment 5

The last patient was enrolled on CCI. Upon implementation of Protocol Amendment 5, a total of 48 patients were enrolled in the dose-expansion portion at the time of enrollment closure, and approximately 3 patients total were on study treatment ([Table 2](#)).

Table 2 Dose Expansion Cohorts

Disease Cohort	Enrollment as of Amendment 4 (Approximate)	Enrollment as of Amendment 5 (Approximate)
HL	25	25
CLL	1	1
CLL post BTK**	6	7
Follicular lymphoma	2	2
Mantle cell lymphoma	2	2
Marginal zone lymphoma	1	1
Waldenström’s macroglobulinemia/lymphoplasmacytic lymphoma	1	1
PTCL	9	9
CBCL	0	0

Abbreviations: BCL-2 = B-cell lymphoma-2; BTK = Bruton tyrosine kinase; CBCL = cutaneous B-cell lymphoma;

CLL =chronic lymphocytic leukemia; HL = Hodgkin’s lymphoma; PTCL = peripheral T-cell lymphoma.

**Approximately 10 patients in the CLL post-BTK cohort will have prior BCL-2 inhibitor therapy.

Patients will receive HMPL-523 at the MTD/RP2D, which has been determined to be 700 mg once daily, in every 28-day treatment cycle until disease progression, death, intolerable toxicity, at investigator’s discretion that the patient can no longer benefit from the study treatment, patient withdrawal from the study, or the end of the study, whichever comes first.

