6.2.2 Serious Adverse Events

An SAE is any AE that meets any of the following criteria:

- Fatal (ie, the AE actually causes or leads to death, except for deaths caused by the progress of the disease)
- Life threatening (ie, the AE, in the view of the investigator, places the patient at immediate risk of death; it does not refer to an event that hypothetically might have caused death if it were more severe)
- Requires or prolongs inpatient hospitalization (excluding emergency or outpatient treatment)

- Results in persistent or significant disability/incapacity (ie, the AE results in substantial disruption of the patient's ability to conduct normal life functions)
- A congenital anomaly/birth defect in a neonate/infant born to a female patient or female partner of a male patient exposed to the investigational product(s)
- Considered a significant medical event by the investigator (eg, may jeopardize the patient or may require medical/surgical intervention to prevent one of the outcomes listed above)

All AEs that do not meet any of the criteria for serious should be regarded as nonserious AEs.

The terms "severe" and "serious" are not synonymous. Severity refers to the intensity of an AE (as in mild, moderate, or severe pain); the event itself may be of relatively minor medical significance (such as severe headache). "Serious" is a regulatory definition and is based on patient or event outcome or action criteria usually associated with events that pose a threat to a patient's life or vital functions. Seriousness (not severity) serves as the guide for defining regulatory reporting obligations.

Severity and seriousness should be independently assessed when recording AEs and SAEs on the CRF.

SAEs are required to be reported by the investigator to the sponsor immediately (ie, no more than 24 hours after learning of the event; see Section 6.5.1 for reporting instructions and Section 6.3.1 for AE reporting period).

All SAEs will be followed until resolution, stabilization, the event is otherwise explained, or the participant is lost to follow-up. Depending on the event, follow-up may require additional tests or medical procedures as indicated and/or referral to a general physician or a medical specialist. All pregnancies that occur during participation in the study should be followed to determine the outcome of the pregnancy.

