6.4 Procedures for Recording Adverse Events

Investigators should use correct medical terminology/concepts when recording AEs or SAEs on the CRF. They should avoid colloquialisms and abbreviations.

All AEs (including SAEs) should be recorded on the AE CRF, and the check box for “Serious” should be ticked for entries that fit the criteria of serious. The investigator should also complete an SAE reporting form and submit this to the sponsor or the sponsor’s designee within 24 hours of knowledge of the event.

Only 1 AE term should be recorded in each event field on the CRF.

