## 17.2. ADVERSE EVENTS

Treatment-emergent adverse events (TEAEs) are defined as AEs with an onset date on or after the first dose of study medication and no later than 30 days after the date of last study treatment administration or start of a new treatment of anti-neoplasm therapy, whichever is earlier. An exception is that study medication related SAE collected later than 30 days after the last treatment date or start of a new treatment of anti-neoplasm therapy will be treated as TEAEs.

Refer to [Section 7.9](#) for handling of partial dates for AEs. In the case where it is not possible to classify an AE as treatment-emergent or not, the AE will be classified as treatment-emergent.

An overall summary of AEs will include the number of patients with:

- Any AE
- Any TEAE
- Any TEAE of CTCAE Grade 3 or higher
- Any TEAE of CTCAE Grade 3
- Any TEAE of CTCAE Grade 4
- Any TEAE of CTCAE Grade 5
- Any Treatment Related TEAE
- Any Treatment Related TEAE of CTCAE Grade 3 or higher
- Any Treatment Related TEAE of CTCAE Grade 3

HMPL-523

- 
- Any Treatment Related TEAE of CTCAE Grade 4
  - Any Treatment Related TEAE of CTCAE Grade 5
  - Any Serious TEAE
  - Any Serious TEAE of CTCAE Grade 3 or higher
  - Any Serious TEAE of CTCAE Grade 3
  - Any Serious TEAE of CTCAE Grade 4
  - Any Serious TEAE of CTCAE Grade 5
  - Any Treatment Related Serious TEAE
  - Any Treatment Related Serious TEAE of CTCAE Grade 3 or higher
  - Any Treatment Related Serious TEAE of CTCAE Grade 3
  - Any Treatment Related Serious TEAE of CTCAE Grade 4
  - Any Treatment Related Serious TEAE of CTCAE Grade 5
  - Any TEAE Leading to Dose Reduction
  - Any TEAE Leading to Drug Interruption
  - Any TEAE Leading to Drug Discontinuation
  - Any TEAE Leading to Death
  - Any TEAE of Special Interest (AESI)

Listings will include the following:

- All AEs
- All SAEs
- AEs leading to Drug Discontinuation
- AEs Leading to Death
- All AESIs

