### 17.2.7. SERIOUS ADVERSE EVENTS

Treatment-emergent serious adverse events (TESAEs) are those TEAEs which are recorded as “Serious” on the Adverse Events page of the eCRF. A summary of serious TEAEs by SOC and PT will be presented by descending total frequency of SOC and descending total frequency of PT within SOC. TEAEs with a missing seriousness to study medication will be regarded as an SAE.

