### 17.3. DEATHS

If any deaths are recorded on the "Death Details" page of the eCRF, the information will be presented in a summary table by stage 1 (dose level) and stage 2 (malignancy type) and a data listing.

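### Deaths due solely to lymphoma progression are kept off the AE page by Protocol 6.4.6 but made Grade 5 SAEs by 6.4.8, and SAP 17.2 has no rule for them

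*Protocol*

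**What the plan says.** Four protocol sections and three SAP sections bear on this.

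- **Protocol 6.2.2** defines a fatal SAE "except for deaths caused by the progress of the disease".
- **Protocol 6.4.6** covers deaths in the AE reporting period. Those the investigator attributes "solely to progression of hematological malignancy under current investigation should be recorded only on the Study Completion/Early Discontinuation CRF". All other on-study deaths go on the AE CRF.
- **Protocol 6.4.8** says worsening or progression of the malignancy is not an AE or SAE unless it directly leads to death, "in which case the disease progression should be reported as a CTCAE Grade 5 SAE".
- **Protocol 6.4** adds "All AEs (including SAEs) should be recorded on the AE CRF".
- **SAP 17.2** lists overall counts of TEAEs by grade, including Grade 3 or higher and Grade 5, of serious TEAEs, and of "Any TEAE Leading to Death". It does not mention progression terms.
- **SAP 17.2.7** takes seriousness from the AE page: "Treatment-emergent serious adverse events (TESAEs) are those TEAEs which are recorded as" serious there.
- **SAP 17.3** handles deaths from a separate Death Details page, where "the information will be presented in a summary table by stage 1 (dose level) and stage 2 (malignancy type) and a data listing".

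**The concern.** The protocol uses three different wordings for the link between progression and death: caused by (6.2.2), solely attributed to (6.4.6) and directly leading to (6.4.8). They do not mark out separate cases. Two sites with the same kind of death can therefore record it in opposite ways, each correctly under one section.

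The SAP carries this into the tables. The all-cause Grade 5, Grade 3 or higher, serious and fatal TEAE rows may then contain some progression deaths and omit others. The SOC/PT tables show a progression term only if someone entered one on the AE page, so a death recorded only on the completion form leaves no trace in them.

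This matters more here than in many trials. The patients have relapsed or refractory lymphoma and have exhausted approved options, and treatment stops at progression (Protocol 5.7.3). Progression can therefore easily fall inside or close to the TEAE window.

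**Working it through.** There is no planned figure to reproduce. The check is a comparison of the texts, followed by a simple calculation of scale.

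**Step 1: one death, two instructions.** Take a death in the AE reporting period that the investigator attributes solely to lymphoma progression.

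| Section | Is the condition met? | Instruction |
|---|---|---|
| Protocol 6.2.2 | Yes | Not serious under the fatal criterion |
| Protocol 6.4.6 | Yes | Completion form only |
| Protocol 6.4.8 | Yes, since a death due only to progression is one that progression directly led to | Grade 5 SAE |
| Protocol 6.4 | Yes, if it is an SAE | AE CRF |

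Section 6.2.2 narrows only one seriousness criterion. The direct clash is between 6.4.6 and 6.4.8 read with 6.4, and it would stand without 6.2.2.

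**Step 2: does other text settle it?**

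- The last sentence of 6.4.8 sends doubtful cases to AE reporting. It does not reach a death the investigator is sure was due to progression alone.
- Protocol 6.2.1 excludes from the AE definition the cases described in 6.4.8, which leads back to the Grade 5 rule.
- Protocol 7.3.3.2 and the subsections of SAP 17.2 neither include nor exclude progression terms.

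**Step 3: which events can move a count.** Under SAP 17.2 the onset must lie between first dose and 30 days after the last dose or the start of new anticancer therapy, whichever is earlier. Later progression deaths do not enter.

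**Step 4: size.** The protocol states that "a total of 48 patients were enrolled in the dose-expansion portion at the time of enrollment closure". Table 2 agrees:

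25 (HL) + 1 (CLL) + 7 (CLL post-BTK) + 2 (FL) + 2 (MCL) + 1 (MZL) + 1 (WM/LPL) + 9 (PTCL) + 0 (CBCL) = 48.

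For k patients whose progression death is recorded under one rule and not the other, the shift in a row is at most k/n.

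| Group | n | Shift for k = 1 (percentage points) |
|---|---|---|
| Stage 2 overall | 48 | 1/48 = 2.1 |
| HL | 25 | 1/25 = 4.0 |
| PTCL | 9 | 1/9 = 11.1 |
| CLL post-BTK | 7 | 1/7 = 14.3 |

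The documents do not give k. If k is assumed to be 1 to 5 in Stage 2, the overall shift is at most 1/48 = 2.1 to 5/48 = 10.4 points. A patient who already counts in a row, for example through another serious TEAE, does not move it.

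**The case against.** The strongest reply is that the gap is narrow and partly visible in the planned outputs. Mixed or doubtful deaths go to the AE page under both 6.4.6 and the last sentence of 6.4.8, so only deaths clearly due to progression alone are in dispute. SAP 17.3 gives a death table and listing from its own page, and SAP 17.2 lists AEs leading to death. Comparing the two listings would show which deaths are missing from the AE page.

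Nor is inconsistent recording demonstrated. The CRFs and their completion guideline are not among the documents and may have told sites what to do. Protocol 2.2.4.8 reports 1 fatal SAE in this study as of 10 May 2022, so the number affected could be small or zero. The primary safety outcome, DLTs, is confined to Cycle 1 and excludes events clearly unrelated to the drug.

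Much of this stands. It limits the consequence to a few all-cause rows and leaves the number of affected patients unknown. It does not remove the conflict for the case that remains. A comparison by hand lets a careful reader find the discrepancy, but the summary counts would still mix two rules. The fatal SAE figure comes from an early cut-off and, by construction, omits any death recorded only on the completion form, so it cannot show that k is small.

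**Conclusion.** The concern holds. For a death due solely to lymphoma progression, Protocol 6.4.6 and 6.4.8 give instructions that cannot both be followed, and SAP 17.2 has no rule that would make its counts consistent.

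The affected rows are the all-cause Grade 5, Grade 3 or higher, serious and fatal TEAE counts. Total deaths, the treatment-related Grade 5 rows and PFS are largely unaffected. The percentages per patient assume that everyone in Table 2, whose counts are labelled approximate, received at least one dose and so belongs to the FAS. Other fatal AEs still reach the AE page, so only the contribution from progression moves.

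This should be corrected before database lock. It does not threaten the trial's main conclusions.

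**What to change.** 1. **Protocol.** Reconcile 6.2.2, 6.4.6 and 6.4.8 to one rule. This review does not say which.
2. **Before database lock.** Check two sets of records against the Death Details page: every Grade 5 or fatal AE with a progression term, and every death recorded only on the completion form. Classify all progression deaths the same way. This assumes that the Death Details page holds a cause of death, which the documents do not state.
3. **SAP 17.2.** Add a sentence on progression terms, and present the Grade 5, Grade 3 or higher, serious and fatal TEAE counts both including and excluding deaths due solely to progression. State which date decides whether a death recorded only on the completion form falls in the TEAE window, since it has no AE onset date.
4. **SAP 17.3.** Give progression deaths their own row.

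The cost is a query on what should be few records, a short SAP addition, a few table rows and a protocol clarification. No new assessments are needed. If the sponsor settles on the 6.4.8 rule, sites with deaths recorded only on the completion form would also owe late AE entries and SAE forms. Enrollment is closed, so a protocol clarification cannot change past recording, and the record check is the step that makes the tables consistent.

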6.4.9 Hospitalization, Prolonged Hospitalization, or Surgery

Any AE that results in hospitalization or prolonged hospitalization should be documented and reported as an SAE unless specifically instructed otherwise in this protocol.

There are some hospitalization scenarios that do not require reporting as an SAE when there is no occurrence of an AE. These scenarios include a planned hospitalization or prolonged hospitalization to:

- Perform an efficacy measurement for the study
- Undergo a diagnostic or elective surgical procedure for a pre-existing medical condition that has not changed
- Receive scheduled therapy for the target disease of the study

In addition, hospitalization due solely to the progression of underlying lymphoma should not be reported as an SAE (Section 6.2.2).

All hospitalizations (including any overnight stay in an acute care hospital) should also be documented on the medical source document with the admission and discharge dates.

6.4.10 Pregnancy

If a female patient becomes pregnant while receiving the study drug or within 30 days after the last dose of investigational product, a pregnancy report should be reported within 24 hours of

learning of the pregnancy to the sponsor's drug safety department or the sponsor's designee. Pregnancy should be recorded on the pregnancy CRF but not the AE CRF.

Male patients must also be instructed to immediately inform the investigator if their partner becomes pregnant during the study or within 30 days after the male patient's last dose of the study drug. If such an event occurs, it should be reported as described above.

Spontaneous abortion should always be classified as an SAE (as the sponsor considers these medically significant), recorded on an AE CRF, and expeditiously reported to the sponsor or the sponsor's designee (see Section 6.5.1).

Any congenital anomaly/birth defect in a neonate/infant born to a mother exposed to the study drug should be classified as an SAE, recorded on the AE CRF, and expeditiously reported to the sponsor or the sponsor's designee (see Section 6.5.1).

After the study period, abortions, congenital anomalies/birth defects, and pregnancy outcomes should still be reported expeditiously to the sponsor or the sponsor's designee.

6.5 Expedited Reporting From Investigator to Sponsor

Certain events require immediate reporting to allow the sponsor to take appropriate measures to address potential new risks in a clinical trial. The investigator must report such events on specific reporting forms to the sponsor (see form completion guideline for contact detail) immediately; under no circumstances should reporting take place more than 24 hours after the investigator learns of the event. The following is a list of events that the investigator must report to the sponsor within 24 hours after learning of the event, regardless of relationship to the study drug:

- SAEs (see Section 6.5.1 for further details)
- Nonserious AEs of special interest (see Section 6.5.1 for further details)
- Pregnancies

6.5.1 Reporting Requirements for All Serious Adverse Events and Protocol-Defined Events of Special Interest

Investigators will submit reports of all SAEs and protocol-defined events of special interest, regardless of attribution, to the sponsor or the sponsor's designee via fax or email within 24 hours of learning of the events.

For initial SAEs and protocol-defined events of special interest reports, investigators should record all case details that can be gathered within 24 hours on a SAE reporting form. Relevant follow-up information should be submitted to the sponsor or the sponsor's designee as soon as it becomes available and/or upon request within 24 hours of the investigator's awareness of the events.

Investigators must also comply with local requirements for reporting SAEs to the local health authority and IRB/IEC.

6.5.2 Regulatory Reporting Requirements for Serious Adverse Events

Prompt notification of SAEs by the investigator to the sponsor is essential so that legal obligations and ethical responsibilities towards the safety of patients are met.

The sponsor has a legal responsibility to notify both the local regulatory authority and other regulatory agencies about the safety of a product under clinical investigation. The sponsor will comply with country-specific regulatory requirements relating to safety reporting to the regulatory authority, IRB/IEC, and investigators.

Investigator safety reports are prepared for suspected unexpected serious adverse reactions according to local regulatory requirements and sponsor policy and are forwarded to investigators as necessary.

An investigator who receives an investigator safety report describing a SAE(s) or other specific safety information (eg, summary or listing of SAEs) from the sponsor will file it with the IB and will notify the IRB/IEC, if appropriate according to local requirements.

6.6 Type and Duration of Follow-up of Patients After Adverse Events

The investigator should follow up all unresolved AEs (including SAEs and DLTs) until the event resolves to baseline grade, the event is assessed by the investigator as stable, new antitumor treatment is initiated, the patient is lost to follow-up, the patient withdraws from the study, or it has been determined that the study treatment or participation is not the cause of the AE. During the study period, resolution of AEs (with dates) should be documented on the AE CRF and in the patient's medical record to facilitate source data verification (SDV).

All pregnancies that occur during the study should be followed to determine their outcome.

For some SAEs, the sponsor or the sponsor's designee may follow-up by telephone, fax, email, and/or a monitoring visit to obtain additional case details deemed necessary to appropriately evaluate the SAE report (eg, hospital discharge summary, consultant report, or autopsy report).

